Rationale / context	
The management of swallowing disorders requires a good understanding of the mechanisms or structures causing the disorder. Clinical assessment lacks precision and diagnostic reliability. Imaging examinations, although more accurate, are still based on the subjective analysis of the examiner, lack standardisation and require human and technical resources that are often inaccessible to the clinician.
 
In this context, ultrasound, which can be performed at the patient's bedside, is non-invasive, non-irradiating and allows the qualitative and quantitative evaluation of the different structures involved in swallowing, opens up new evaluation perspectives.

Main Objective	To construct an ultrasound score to diagnose swallowing disorders in at-risk patients attending a day hospital.
Secondary objectives	
 - To evaluate the validity and reliability of a new ultrasound score for the diagnosis of swallowing disorders. - To assess the reliability and validity of hyoid bone ascension in the diagnosis of swallowing disorders; - To evaluate the reliability and validity of the digastric muscle thickening fraction in the diagnosis of swallowing disorders; - To evaluate the reliability and validity of the genohyoid thickening fraction in the diagnosis of swallowing disorders; - To assess the reliability and validity of the amount and duration of lingual movement in the diagnosis of swallowing disorders.
Research scheme	Prospective, monocentric, interventional cohort study with minimal risks and constraints falling within the scope of article L.1121-1 of the Public Health Code.
Inclusion criteria	
 - Patients admitted to the day hospital ; - Patients with a medical indication for videofluoroscopy; - Medical prescription for physiotherapy assessment; - Ultrasound operator available; - Patient at least 18 years old at the time of inclusion; - Affiliation with a social security scheme or beneficiary of such a scheme ; - Oral, free, informed and express consent of the patient.
Non-inclusion criteria	
 - Patient with total laryngectomy ; - Patient's refusal to participate in the study ; - Known pregnancy ; - Person subject to a legal protection measure ; - Cognitive impairment incompatible with understanding instructions; - Patient under guardianship or curatorship ;

	- Patient in care limitation.
Primary endpoint	Selection of the variables composing the score based on their diagnostic accuracy and their contribution to the predictive model.
Secondary evaluation criteria	
 - To evaluate the reproducibility and diagnostic accuracy of the ultrasound score in the diagnosis of swallowing disorders; - To evaluate the reproducibility and diagnostic accuracy of hyoid bone ascension in the diagnosis of swallowing disorders; - To evaluate the reproducibility and diagnostic accuracy of the digastric muscle thickening fraction in the diagnosis of swallowing disorders; - To evaluate the reproducibility and diagnostic accuracy of the genohyoid thickening fraction in the diagnosis of swallowing disorders; - To evaluate the reproducibility and diagnostic accuracy of the amount and duration of lingual movement in the diagnosis of swallowing disorders.
Comparison groups	Videofluoroscopy will be used as a reference examination.
Number of subjects needed	100
Expected number of centres	1
Duration of the research	25 months
Statistical analysis of data	
Univariate comparisons will use the usual statistical tests after verification of the distribution of the variables (Chi2 or Fisher's test, t-test, anova or their non-parametric equivalents Wilcoxon and Kruskal-Wallis tests). The ultrasound variables will be compared between the 2 groups by the appropriate tests according to the type of variables (quantitative or qualitative) and their distribution. The selection of variables in the prediction model will be performed by multivariate logistic regression based on the AIC.
 
The study of inter and intra-examiner reproducibility will be evaluated with the Kappa coefficient. The threshold of the ultrasound score defining the presence of swallowing disorders will be determined using ROC (Receiver Operating Characteristic) curve analysis. Sensitivity, specificity, positive and negative predictive values, positive and negative likelihood ratios and the diagnostic ODD-Ratio will be estimated.

Expected benefits	We expect excellent reliability and validity of ultrasound in the diagnosis of swallowing disorders, which would make it possible to propose an alternative examination to videofluoroscopy that would be more easily performed on an outpatient basis, non-invasive and non-irradiating.
Source of funding	Forcilles Hospital-Cognacq-Jay Foundation
Independent Supervisory Committee planned	No

LIST OF ABBREVIATIONS

1.1 Swallowing disorders

Swallowing is the mechanism that allows food to be grasped, prepared in the oral cavity and then propelled from the oropharynx to the stomach while protecting the airways. This is a complex semi-reflexive sensory-motor mechanism involving many functions and anatomical structures. It involves more than fifty muscles, six cranial pairs and cortical structures, including the fronto-parietal operculum, the primary sensorimotor cortex and the anterior insula association. (1)

Impairment of any of these functions or structures of swallowing, whether neurological, muscular or mechanical, resulting in partial or total inability to transport the bolus of food to the lower digestive tract is called dysphagia or swallowing disorder.

In some clinical contexts, the particularly high prevalence of these disorders motivates the quasi-systematic screening of patients. This is the case, for example, in intensive care, ENT oncology and post-stroke. (2)(3)

The presence of swallowing disorders can lead to undernutrition, dehydration or the development of inhalation pneumonitis. (4)(5) These complications related to swallowing disorders are associated with an increase in patient morbidity and mortality, mainly in terms of increased length of stay, hospital costs, readmission rates and mortality. (6)(7)(8)

The complexity of the swallowing mechanism, as well as the lack of specificity of the symptoms often encountered, requires a multidisciplinary assessment (9). The lack of precision of clinical tests will require the use of additional imaging or endoscopy. (6)(10)

1.1. Background to the onset of swallowing disorders

Swallowing disorders, although under-diagnosed (8) The prevalence of swallowing disorders, although under-diagnosed, can be as high as 30% in hospitalised patients. (11) This prevalence is particularly high in certain clinical situations such as neurological disorders or diseases like Parkinson's disease (80%) (12) neuromuscular diseases (80%) (13) or post-stroke (81%) (14). In head and neck cancers, especially after surgery, the prevalence can be as high as 61%; (15). In intensive care, they may be the consequence of intubation, tracheotomies and prolonged mechanical ventilation, (16)(17)(7) or even the reason for admission to the intensive care unit. (18)(5)

1.2 Day hospital for swallowing disorders

Dysphagia is a historically important disorder at Forcilles because of its prevalence in the population admitted to hospital. Various health professionals are organised around the multidisciplinary management of these disorders in the different departments of the hospital. The need to bring together this expertise, in order to meet the growing demand from independent professionals and other surrounding health establishments, in particular the geriatric, acute medicine and ENT cancer departments, led to the creation of a swallowing day hospital (HDJ).

Most patients admitted to HDJ have sarcopenia, ENT cancers and/or have had long periods of mechanical ventilation and may still have a tracheostomy.

The HDJ therefore welcomes patients with the risk factors described above for swallowing disorders. The examinations that will be carried out are prescribed by the doctor responsible for the medical care of the patient.

The following equipment is available in the HDJ: an endoscopy column and the medical equipment necessary to monitor the patient's vital parameters; a radiology room with the necessary equipment for videofluoroscopy and two consultation rooms. Thus, within this HDJ, a doctor is involved, responsible for the unit, who ensures the medical evaluation of the patient, the carrying out of medical examinations when they are indicated and the submission of the end of hospitalisation report; a radiologist doctor who ensures the carrying out of imaging examinations; physiotherapists and speech therapists in charge of the clinical assessment of the patient and dieticians who carry out a consultation in order to detect and manage any undernutrition, and also to adapt the patient's diet to the food textures recommended by the speech therapists following their assessment.

1.3 Diagnostic strategy for swallowing disorders

1.3.1 Clinical assessment

Clinical assessment of swallowing includes analytical evaluation of the structures involved and the use of composite tests or feeding trials. The clinician may also use self-report questionnaires to assess the patient's feelings to guide exploration. (19)

As part of the analytical assessment, the speech and language therapist, after reading the medical record and interviewing the patient, assesses structures such as the lips, cheeks and tongue, and explores the cranial nerves and reflexes involved in swallowing. (20)(21)

He will also assess the pharyngeal phase during palpation of the larynx and cervical auscultation during swallowing. (22)

For feeding trials, many standardised tests are described in the literature. They are based on a swallow test and the clinician's identification of signs such as coughing, oxygen desaturation or voice changes, which may indicate inhalation. (20) These tests differ in the amount of test food administered, the variability of its texture, and their methodology.

Many studies have assessed the validity of these tests and the clinical examination for swallowing disorders. The majority of these studies have focused on screening in a post-stroke patient population, thereby validating some of these tests in this patient population. (23)(24) Several reviews of the literature have been carried out in recent years and all agree on the heterogeneity of the studies, the large number of existing assessment methods and the lack of a standardised test with sufficient predictive value in different populations such as neurological and neuromuscular diseases, cancers of the ENT sphere, in elderly subjects or in intensive care patients (8)(10)(13)(25).

Furthermore, these assessments remain based on the feeding trial and do not allow for the diagnosis of deficiencies in the structures and functions involved in swallowing and therefore to orientate the therapeutic strategy.

1.3.2 Radiology and fibroscopy

The literature agrees that videofluoroscopy (VFSS) and swallowing fibroscopy are the gold standards for swallowing assessment. (26)(27) Different quantities and textures, which will evolve progressively according to the outcome of the first feeding trials, will be used to assess the patient's swallowing abilities.

Real-time visualization of swallowing will allow the clinician to objectify inhalation as a sign of a swallowing disorder (28) and to estimate its severity by means of scores such as the "Dysphagia outcome and severity scale" (DOSS) or the "Penetration-Aspiration Scale" (PAS). (29)(30)(31) (**Appendices 1 and 2**).

For VFSS, the liquids/foods administered to the patient are mixed with barium in order to follow the course of the food bolus. This allows the assessment of all three phases of swallowing and a better assessment of the oral phase compared to nasofibroscopy of swallowing (FEES). However, it does not allow the analysis of the anatomy of structures and requires the patient to be transported to an equipped room and exposed to radiation.

The FEES, thanks to its location at the tip of the epiglottis during the examination, has the advantage of allowing the evaluation of tissues, possible local trauma or the presence of secretions. In addition, it allows the evaluation of the sensitivity of the larynx. However, this examination is often uncomfortable for the patient and requires the frequent use of a local anaesthetic which alters sensitivity. (6) Physiological movements during swallowing make it

difficult to see the vocal cords. The examiner will have to lower the fiberscope afterwards to look for signs of inhalation. Furthermore, there is a lack of a standardised protocol. (32)

1.3.3 Ultrasound evaluation

It allows the qualitative and quantitative assessment of the structures involved in the three phases of swallowing: the strength of the tongue, the kinetics of the lingual propulsion, the thickness of the supra- and infra-hyoid muscles at rest and during swallowing, the ascent of the hyoid bone and the larynx, and the mobility and diameter of the upper esophageal sphincter.

The application of ultrasound in swallowing assessment has been described for many years. (33) It is an easy to use, reproducible, bedside tool that is non-invasive and non-irradiating.

Ultrasound assesses the kinetics of the tongue for abnormal movements and the contractility and thickness of the oropharyngeal muscles to diagnose possible dysfunction. (34)(35)

Ultrasound will allow quantitative and qualitative analysis of lingual kinetics during swallowing, in particular looking for abnormal movement patterns. (36)(37)

It is also possible to quantify the movement in search of a propulsion defect. (38)(39) It also allows qualitative and quantitative assessment of the geniohyoid, mylohyoid and digastric muscles.

The thickness of these muscles at rest and during swallowing and their echogenicity can be quantified.(40)(41) The measurement of the thickness of these muscles is reproducible and its accuracy in assessing the digastric muscles has been compared with MRI, showing a very good correlation. (42)(45)

During this second phase of swallowing, it will also be possible to measure the duration and distance of hyoid bone elevation, reflecting laryngeal elevation. (43)(44)(45) A decrease in hyoid bone elevation associated with a decrease in lingual contraction capacity as seen on ultrasound can explain dysphagia. (46)

Finally, ultrasound can be used to assess the displacement and diameter of opening and closing of the upper oesophageal sphincter (USO), allowing the detection of dysphagia related to USO damage. (47)

This ultrasound evaluation will complement the clinical evaluation of reflexes, cranial pairs or the patient's posture or vigilance, with a quantitative analysis of the structures mentioned above, for which the clinical examination lacks precision and reliability and needs to be supplemented by complementary examinations. (48)(49)

This quantitative, reproducible, non-invasive, non-radiating, bedside ultrasound analysis represents a promising tool for clinical practice to monitor patient progress. (50)

Numerous studies have investigated the use of ultrasound as a diagnostic tool for swallowing disorders in different patient populations. (43)(51)(52) However, these studies are limited by their small size, often include healthy subjects, do not usually define a threshold value necessary for diagnosis and do not combine the evaluation of the different structures involved in swallowing.

1.4 Research hypothesis

We hypothesise that an ultrasound score is reliable and valid in the assessment of swallowing disorders in at-risk patients admitted to the swallowing day hospital.

2 Objective

2.1 Main objective

The main objective of this study is to construct an ultrasound score to diagnose swallowing disorders in at-risk patients attending a day hospital.

2.2 Secondary objectives

In at-risk patients admitted to a day hospital Swallowing :

- To evaluate the validity and reliability of a new ultrasound score for the diagnosis of swallowing disorders.
- To assess the reliability and validity of hyoid bone ascension in the diagnosis of swallowing disorders;
- To evaluate the reliability and validity of the digastric muscle thickening fraction in the diagnosis of swallowing disorders;
- To evaluate the reliability and validity of the genohyoid thickening fraction in the diagnosis of swallowing disorders;
- To assess the reliability and validity of the amount and duration of lingual movement in the diagnosis of swallowing disorders.

3 Outcome

3.1 Primary outcome

The main outcome is the selection of the variables composing the score based on their diagnostic accuracy and their contribution to the predictive model.

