9.2 General aspects

Descriptive statistics will be based on means (+/- standard deviation) or medians [minimum-maximum] depending on the distribution of quantitative variables. Qualitative variables will be described in terms of numbers and percentages. Univariate comparisons will use the usual statistical tests after verification of the distribution of the variables (Chi2 or Fisher's test, t-test, anova or their non-parametric equivalents Wilcoxon and Kruskal-Wallis tests).

The tests will be performed at the 5% significance level. The 95% confidence intervals will be provided for each estimate.

Measures of association between quantitative variables will be made using Pearson's or Spearman's correlation coefficients depending on the distribution of the data. Measures of association between qualitative variables will be performed using the Chi-square or Fisher test depending on the distribution of the data.

The agreement between quantitative variables will be evaluated using the Bland-Altman method and that between qualitative variables using the Kappa coefficient.

Calculations will be made using IBM SPSS v21 and R software (version 3.6.1, www.R-project.org).

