9.5 Selection of variables to be included in the score

Patients will be classified into 2 groups according to the diagnosis obtained with VFSS: positive group (presence of swallowing disorders) and negative group (absence of swallowing disorders). The ultrasound variables will be compared between the 2 groups by appropriate tests according to the type of variables (quantitative or qualitative) and their distribution. The results of these comparisons will be used to select the ultrasound variables showing a difference between the 2 groups ($p < 0.20$) for inclusion in the multivariate logistic regression. (62)(63)

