9.6 Weighting of variables

The previously selected ultrasound variables will be included in the model predicting the presence of swallowing disorders. Multiple logistic regression with variable selection using the Akaike information criterion (AIC) method will be used. The presence of multicollinearity between variables will also be investigated and the variable eliminated if necessary.

Variables that do not improve the predictive model will thus be removed from the score.

The scores for each variable resulting from the multivariate logistic regression will be used to weight each variable in the ultrasound score. (62)(63)

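### The primary outcome is a list of selected variables with no criterion for a negative result, and the selection rules often return a score from uninformative variables

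*Combined protocol and SAP*

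**What the plan says.** The main objective is one of construction: "The main objective of this study is to construct an ultrasound score to diagnose swallowing disorders in at-risk patients attending a day hospital" (2.1). The primary outcome follows it: "The main outcome is the selection of the variables composing the score based on their diagnostic accuracy and their contribution to the predictive model" (3.1). The research hypothesis goes further: "We hypothesise that an ultrasound score is reliable and valid in the assessment of swallowing disorders" (1.4). Validity and reliability appear as secondary objectives and outcomes (2.2, 3.2).

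The selection procedure has three steps.

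- **9.4, cut-points.** A quantitative variable that is linear in the logit is dichotomised at the ROC threshold found in the study data. Otherwise it is split into classes.
- **9.5, screen.** The group comparisons serve to "select the ultrasound variables showing a difference between the 2 groups ($p < 0.20$) for inclusion in the multivariate logistic regression". The variables are to be "compared between the 2 groups by appropriate tests according to the type of variables (quantitative or qualitative) and their distribution", which leaves open whether the raw or the already dichotomised value is tested.
- **9.6, AIC.** "Variables that do not improve the predictive model will thus be removed from the score".

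Section 9.2 gives a general rule, "The tests will be performed at the 5% significance level", and promises a 95% confidence interval for each estimate. Section 9.7.2 chooses a score threshold by ROC analysis and computes sensitivity, specificity, predictive values and the diagnostic odds ratio. It sets no minimum value and plans no correction for optimism. No section says what is reported if no variable survives.

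**The concern.** A list of variables is the product of a procedure, not a quantity with an estimate, an interval and a value that would count as failure. Both filters are liberal: p<0.20, then AIC, which keeps a one-parameter term at about p<0.157. Several candidates pass through them, and cut-points may already have been tuned to the same VFSS result. Noise can therefore fill the list.

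The protocol expects the score to support ultrasound as an alternative to videofluoroscopy (sections 10 and 11.2). If a score built from noise is a common outcome, the primary result says little about whether the hypothesis in 1.4 is true. The accuracy measures that could contradict it are secondary, have no target, and are computed on the data that built the score. This differs from the point that apparent accuracy is optimistic: correcting the secondary estimates alone would still leave the primary outcome with no way to be judged negative.

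**Working it through.** **Inputs from the protocol.** Five variables, 50% prevalence and ten events per variable (9.1); ten candidate rows in the table of 9.3 (six with a threshold, three yes/no, one Heckmatt grade); p<0.20 (9.5); AIC (9.6).

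**The plan's own figure.** 5 variables × 10 events / 0.50 = 100 patients, as stated. This gives 50 positive and 50 negative patients. Because 9.1 counts five variables and 9.3 lists ten, both are shown.

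**Closed form with no cut-point search, independent uninformative candidates.** AIC keeps a one-parameter term if its likelihood-ratio chi-square exceeds 2, and P(chi-square on 1 df > 2) = 0.1573.

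- At least one kept by AIC alone: 1 − 0.8427^5 = 57.5%; 1 − 0.8427^10 = 81.9%.
- At least one passing the screen alone: 1 − 0.8^5 = 67.2%; 1 − 0.8^10 = 89.3%.

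**Simulation of the full rules when nothing is informative.** Assumptions that the protocol does not supply: all candidates quantitative; common correlation 0, 0.3 or 0.6; every quantitative variable dichotomised at its ROC optimum where a cut-point is used; backward AIC. There were 1,000 runs for five candidates. For ten there were 1,000 in the first row and 400 in the others. Simulation error is about 1.6 points for five candidates and up to 2.4 for ten. Cells give the share of trials with a non-empty score at correlation 0 / 0.3 / 0.6.

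| Reading | Five candidates | Ten candidates |
|---|---|---|
| Screen raw values, keep continuous | 61.0 / 54.5 / 44.9% | 79.8% (correlation 0 only) |
| Screen raw values, then cut-point, then AIC | 69.2 / 62.7 / 53.3% | 84.8 / 80.0 / 67.0% |
| Cut-point, then screen, then AIC (section order) | 99.9 / 99.5 / 99.2% | 100 / 99.8 / 100% |

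In section order the score keeps on average 3.15 / 2.76 / 2.14 noise variables (five candidates) or 4.08 / 3.34 / 2.55 (ten). The median apparent AUC is 0.71 / 0.70 / 0.66 or 0.74 / 0.72 / 0.68.

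**Range over repeat runs.** Further runs under the same kind of assumptions widen the ranges to about 40–70% (five) and 57–92% (ten) with raw screening. In section order they give 99–100%, with median apparent AUC 0.66–0.78. With raw screening the score cannot be non-empty unless something passes the screen, so 67% and 89% are approximate ceilings for independent candidates. The simulated upper ends lie slightly above them, by an amount that simulation error can produce.

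**Mix closer to 9.3.** With six quantitative and four binary noise candidates, independent, raw screening gave 80.5% (kept continuous) and 83.8% (dichotomised afterwards). Section order gave 100%, with median apparent AUC 0.74.

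**Would an ordinary AUC interval expose a noise score?** Not reliably. Under the same null, an uncorrected 95% CI for the apparent AUC lay wholly above 0.5 in 17–61% of trials (continuous) and in 73–99.8% (section order).

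**The case against.** The main objective is to construct a score, and a selection outcome is coherent with that. Validity is assigned to secondary objectives with their own accuracy measures and confidence intervals, and no section says that obtaining a score proves the hypothesis. A liberal entry screen is a deliberate modelling choice. All of this stands, and it is why the fix does not require the primary outcome to be replaced.

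Three stronger readings are tempting but not supported.

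- *The primary result cannot come out negative.* Section 9.6 removes variables that add nothing, so an empty model is possible. With raw screening, five candidates and correlation 0.6, it occurs in up to about 60% of null trials (100 − 40).
- *The selection breaches the 5% level.* Section 9.2 states that level in general terms and does not attach it to the primary outcome, while 9.5 sets its own threshold. Comparing the null selection rate with 5% treats a screen as a confirmatory test.
- *Diagnostic accuracy plays no part.* Section 9.4 sets thresholds by ROC analysis, and 9.5 compares groups defined by VFSS. The narrower statement holds: 9.5 and 9.6 apply no accuracy criterion for keeping a variable, although 3.1 names accuracy as a basis for selection.

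It can also be said that the ultrasound measures are unlikely all to be uninformative. That may be so, but the all-null case is the reference against which a claim of validity has to be judged.

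**Conclusion.** The concern holds in a limited form. The primary outcome has no criterion for a negative result, and the rules often return a score when nothing is informative. The frequency depends mainly on a choice that the plan leaves open. It is about 40–70% (five candidates) or 57–92% (ten) if raw values are screened, and close to certain if cut-points come first. In the second case the noise score also looks moderately accurate.

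The figures rest on 50/50 patients, quantitative noise candidates, correlation 0 to 0.6 and dichotomisation throughout. Splitting into classes and dropping collinear variables were not modelled, because the plan does not define those steps. The conclusion does not need a precise rate: under every reading examined, obtaining a score is little or no evidence that it is valid. This is an inexpensive improvement to the plan, not a reason to reject a development objective.

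**What to change.** Keep variable selection as the construction method and, if the sponsor wishes, as the primary outcome. Then:

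1. In 3.1 and 9.7.2, report the score's AUC against VFSS beside the variable list, with an optimism-corrected estimate and 95% CI from a bootstrap that repeats all of 9.4–9.6. An uncorrected interval is not enough, as shown above.
2. Add one permutation test at 5%: permute the VFSS labels (for example 1,000 times), rerun 9.4–9.6 each time, and compare the observed AUC with that distribution. Claim a diagnostic score only if the test is passed. Passing shows better-than-chance performance only, not equivalence to VFSS.
3. State that if no variable survives, the result is reported as no score.
4. Fix the order of cut-point and screen, and make the linearity check, class splitting and collinearity removal algorithmic so that they can be rerun.
5. In 3.1, either apply the diagnostic-accuracy basis in 9.5–9.6 or delete it.

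**Cost.** More scripting, judgement steps turned into rules in advance, and possibly a protocol modification needing an ethics committee opinion under 13.5. The result can also be negative. No additional patients or measurements are required.
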